Data collection and storage. Research interviews and other relevant data will be collected via the REDCap program behind the VA firewall and stored on a VA server. REDCap allows the assignment of different levels of access privileges and audit trails, thus ensuring proper data management and minimizing mistakes. For instance the Project Manager can be the only one who is allowed to edit data, while RAs can be allowed to enter and download data only. At the time of this IRB amendment (2/9/16), we were given permission to use REDCap while it is under review for VA Research by VACO. If REDCap is disallowed, we will identify and propose alternative systems.

The Relational Agent software is installed on VA tablet/laptops and the database for the program will be on a VA server. The software installed on the tablets includes custom software created by Northeastern University computer scientists, Unity software used for animation, and XXAMP, a web application. Also, the system uses MySQL database on both the tablets and the VA server. It is installed on the tablets for local storage, and as insurance against being unable to run the program if wifi connection is unavailable. It gets backed up to the VA servers. Both the database on tablets and VA server and the transmission to the server can be encrypted.

Study Design for Aim 2

This study is a mixed design, with Alcohol Severity Groups and Treatment Arms as between-groups variables and Time of Testing (Baseline vs. 3-Month Follow-up) as a repeated measure variable. The main focus of this initial RCT is to compare Treatment as Usual (TAU) to TAU plus the Relational Agent Intervention

(TAU+RA) on (a) alcohol consumption, (b) rates of brief intervention, and (c) rates of referral to treatment. We will use a stratified randomization scheme, stratifying on whether a Veteran is a risky drinker or has the more severe designation of an alcohol use disorder, to ensure that the two study groups balance on severity. Veterans allocated to Treatment as Usual will continue to receive all usual care as delivered in the PCC. Veterans allocated to Treatment as Usual plus Relational Agent Intervention will interact with the Relational Agent as soon as possible following the baseline assessment, and still receive usual care.

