Alcohol use and related behaviors will be assessed by in-person survey at baseline and by telephone survey at 3 months after randomization. Principal intervention effect analyses will be performed at 3 months. The primary dependent (outcome) variables are number of drinking days per week (frequency) and average drinks per drinking day (quantity). Secondary dependent variables are percent receiving brief intervention and percent referred for further evaluation or treatment of alcohol problems.

Independent Variables

The two independent variables are the experimental condition, Treatment as Usual vs. Treatment as Usual plus Relational Agent Intervention, and the severity of alcohol use, dichotomized as Risky Drinking vs. Alcohol Use Disorder. The experimental condition will be assigned by random allocation (see Section 4.e.7).

The severity of alcohol use variable, which will be used to allocate Veteran-participants into two strata prior to randomization, will be ascertained by the baseline completion of the MINI.

Dependent Variables

The primary dependent variables (i.e., the main study outcome measures) are **number of drinking days per week** and **average drinks per drinking day**. Because the Relational Agent will target reduction of both the frequency (number of drinking days per week) and the quantity (average drinks per drinking day) of alcohol consumption, each of these measures will be considered separately as primary outcome measures. These variables are measured by the QDS.

Secondary dependent variables include **completion of brief intervention** (yes/no) and **referral for evaluation/treatment** (yes/no); these secondary dependent variables will be ascertained from review of CPRS. We will also ascertain completion of brief intervention and referral for evaluation/treatment from the interviews with participants; we will assess concordance between CPRS and Veterans' self-report and, for main analyses, we will count brief intervention or referral as completed if they are ascertained from either source.

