Other variables that we will use to describe the sample and explore in cross-tabulations with the outcome variables include summary scores from the REALM health literacy questions and .the ECA Questionnaire.

Statistical Analysis

The figure below shows a schematic representation of the research design. For visual clarity, it does not show the descriptive variables mentioned above.

Preliminary Analyses: In preliminary analyses, we will examine the distributions of all dependent variables, and consider appropriate transformations. In particular, we will consider an arcsine transformation (appropriate for reported proportions) for the “number of drinking days per week” and a log transformation (appropriate for highly skewed distributions) for “average drinks per drinking day”. The 4 groups will be tested for any differences in socio-demographic variables. All quantitative variables (e.g. Age) will be tested by 2-way between groups Analysis of Variance (ANOVA); all qualitative variables (e.g. Gender) will be tested by 3-dimensional Chi Square (Mantel-Haenszel test). Any variable found to be significant will be entered into all subsequent analyses as a covariate.

Checks for “non-Response” Bias: The potential for differential drop-out rates among the four groups is itself an interesting and important empirical question, with clinical implications. Drop-out rates will be tested by Chi Square. Factors that may contribute to drop-out rate will be tested by logistic regression. In effect, the four groups can be stratified at Baseline into Completers and non-Completers. Then, these groups will be compared on Baseline values to determine which, if any, are significant systematic “predictors” of Completion.

Statistical Analyses: If there is no significant differential drop-out rate attributable to Alcohol Group, to Treatment Group, or, especially, to Alcohol x Treatment interaction, then the non-completion rate can be considered as a random loss, and Completers as a representative sample. In that case, the dependent variable(s) will be tested by 3-way mixed design AN(CO)VA. If it is determined that there is a differential drop-out rate such that the data are not missing completely at random (NMCAR), then we will utilize a generalized estimation equation (GEE) approach, which should provide an unbiased estimate of the intervention effect.

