GEE utilizes inverse probabilities to correct for any bias associated with NMCAR, with participants who are Completers weighted with the drop-out probabilities of participants with the “same” characteristics at Baseline. These weighting values will be estimated from the logistic analyses described above.

The overall design is a three-way mixed-design with Treatment Arm (Treatment as Usual vs. Treatment as Usual plus Relational Agent Intervention) and Drinking Severity (Risky vs. Alcohol Use Disorder) and 2 occasions (0 and 3 months) as the repeated measures design. We will take an intent-to-treat approach to the analysis; Veterans will be included in our primary analyses regardless of their level of adherence with their assigned intervention. Participants who do not complete the 3-month follow-up assessment will be considered to have missing data for that assessment and will not be included in the analysis of intervention effectiveness. The secondary outcomes, which will be “incidence rates”, will be tested by logistic regression.

Primary Hypothesis: The Relational Agent will be more effective than Treatment as Usual in reducing the quantity and frequency of alcohol use.

Our primary analyses of the effectiveness of Treatment as Usual vs. Treatment as Usual plus Relational Agent Intervention will focus on measurement outcome variables at the **3-month follow-up**. Separate analyses will be performed for the two primary outcome measures: number of drinking days per week (frequency) and average drinks per drinking day (quantity), both reported over a month. Here we describe the analytic approach for the outcome of quantity of alcohol use (average drinks per drinking day); the approach for frequency will be analogous. Initially our analysis will be through analysis of covariance models. We will include baseline values of the outcome variable as a covariate in these models, so our analyses may be interpreted as focusing on the change in outcome from baseline to three month follow-up. If any key characteristics of our sample were found to differ between groups, we will enter those as covariates as well.

Secondary Hypothesis: The Relational Agent will be more effective than Treatment as Usual in improving rates of brief intervention.

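### A test of drop-out rates picks the model for the primary outcomes on an invalid inference, and the rule is not reconciled with the 3-month ANCOVA that the plan calls primary

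*Combined protocol and SAP*

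**What the plan says.** Under Statistical Analysis, the paragraph headed Statistical Analyses sets a rule for the dependent variables in general. If there is "no significant differential drop-out rate attributable to Alcohol Group, to Treatment Group, or, especially, to Alcohol x Treatment interaction", it says, "then the non-completion rate can be considered as a random loss, and Completers as a representative sample", and "the dependent variable(s) will be tested by 3-way mixed design AN(CO)VA". If drop-out is differential, a GEE is used, with completers weighted by inverse probabilities. Of the weights the plan says: "These weighting values will be estimated from the logistic analyses described above".

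The preceding paragraph, on non-response bias, also looks at who drops out. Drop-out factors go into a logistic regression, and completers and non-completers are set side by side: "these groups will be compared on Baseline values to determine which, if any, are significant systematic" predictors of completion.

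The mixed design treats baseline as an outcome occasion. Study Design for Aim 2 has "Time of Testing (Baseline vs. 3-Month Follow-up) as a repeated measure variable", and the overall-design paragraph of Statistical Analysis has "2 occasions (0 and 3 months) as the repeated measures design".

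Three other places point to a different model. Study Design for Aim 2 states: "Principal intervention effect analyses will be performed at 3 months". The Primary Hypothesis paragraph describes the primary analyses as ANCOVA with the baseline value as a covariate. Sample Size and Power Considerations describes the principal analyses in the same way. None of these mentions the drop-out rule.

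**The concern.** There are two problems.

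1. **Precedence.** Three models are named for the same two primary outcomes and none is ranked. With two occasions and no baseline covariate, the treatment test in the mixed design is arm-by-time, which is a comparison of change scores. That is a different test from a 3-month ANCOVA and can give a different verdict on the same data. The Primary Hypothesis paragraph says ANCOVA is used *initially*, but ties that word to no condition.

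2. **Inference.** A non-significant difference in drop-out rates does not show that loss is random. Rates can be equal while the kind of patient lost differs by arm, and a test on 180 people will miss sizeable differences in rate. The comparison of completers with non-completers is better suited to finding such a pattern. It and the logistic analyses inform the GEE weights, but they do not trigger the switch to GEE.

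At stake are a primary test that is not fixed before the data are seen, and a power claim that depends on which test is meant.

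**Working it through.** **Inputs from the plan.** 180 participants, equal arms in the power table (90 per arm), alpha 0.05. Loss of 20%, 25% or 30% leaves 72, 68 (67.5 rounded) or 63 completers per arm. Stated power is 0.84, 0.82 and 0.78.

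**Assumptions.** Effect d = 0.5 for the plan's medium effect, two-sided tests, normal outcomes with equal variances, correlation r between baseline and 3 months, 0.05 for each drop-out test, and no baseline covariate in the mixed model. The plan gives none of these figures.

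**1. The plan's own power.** The noncentrality is δ = d·√(n/2)/√v, with v = 1 for an unadjusted comparison.
- n = 72: 0.5 × √36 = 3.00, power 0.846
- n = 68: 0.5 × √34 = 2.92, power 0.825
- n = 63: 0.5 × √31.5 = 2.81, power 0.795

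These are within 2 points of the table. The calculation uses no baseline correlation, so it does not reveal which model was meant.

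**2. The two models.** Use v = 2(1 − r) for arm-by-time and v = 1 − r² for ANCOVA. For example, at r = 0.3 and n = 72, arm-by-time has δ = 3.00/√1.4 = 2.54 and ANCOVA has δ = 3.00/√0.91 = 3.14.

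| r | Arm-by-time power (72/68/63 per arm) | ANCOVA power (72/68/63 per arm) |
|---|---|---|
| 0.3 | 0.71 / 0.69 / 0.65 | 0.88 / 0.86 / 0.83 |
| 0.5 | 0.85 / 0.83 / 0.80 | 0.93 / 0.92 / 0.90 |
| 0.7 | 0.97 / 0.96 / 0.95 | 0.99 / 0.98 / 0.97 |

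To reach 80% power, arm-by-time needs r of at least 0.43, 0.47 and 0.51. ANCOVA reaches it at any r with 72 or 68 per arm, and at r = 0.11 with 63. In simulated trials with 72 per arm, the two tests disagree on significance in 20% of trials at r = 0.3, about 10% at r = 0.5 and 2% at r = 0.7.

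**3. Strength of the drop-out test** (20% in one arm, 30% in the other, 90 per arm). The plan does not say how its three conditions are tested.
- Two-arm chi-square: power 0.34.
- One four-group chi-square: power 0.22.
- Three separate tests (arm, severity, interaction), any one significant: about 0.40. This reading also signals a difference in about 14% of trials when rates are equal.

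**4. Equal rates, different people.** Simulation with no true effect, 90 per arm, 25% loss in both arms and r = 0.5. The log-odds of dropping out rise or fall by 0.4 to 1.0 per SD of the driver. Entries are absolute bias in SD.

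| Drop-out depends on | Arms affected | Arm-by-time | ANCOVA |
|---|---|---|---|
| Baseline drinking | one arm only | 0.05 to 0.11 | within 0.01 |
| Baseline drinking | opposite directions | 0.10 to 0.21 | within 0.01 |
| 3-month outcome | one arm only | 0.05 to 0.11 | 0.07 to 0.16 |
| 3-month outcome | opposite directions | 0.10 to 0.21 | 0.15 to 0.33 |

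In the baseline-driven rows, arm-by-time type I error is 6% to 9% (one arm) and 9% to 23% (opposite). The two-arm drop-out test is significant in only 4% to 6% of those trials, about its false-alarm rate. A within-arm comparison of baseline drinking between completers and non-completers is significant in 39% to over 99%.

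**5. Weights.** For baseline-driven loss in opposite directions, weights from a drop-out model with arm, stratum and baseline only leave the arm-by-time bias at 0.10 to 0.21 SD. Adding an arm-by-baseline term reduces it to at most 0.006 SD.

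**The case against.** The strongest reply is that the plan does have a primary analysis. The drop-out rule is general, while the two paragraphs that deal specifically with the primary hypothesis and its power both name ANCOVA. The Primary Hypothesis paragraph also says its ANCOVA can be read as an analysis of change. Indeed, regressing change on arm and baseline gives the same arm estimate as the 3-month ANCOVA. If the mixed AN(CO)VA were meant to carry baseline as a covariate, the arm-by-time figures would not apply. The three-way layout may also serve the planned look at each severity stratum. All of this stands, and it makes ANCOVA the likeliest intention. It does not state precedence, and an analyst who followed the drop-out rule literally would run a different model.

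Several stronger readings are tempting, and the documents do not support them.
- *ANCOVA is free of drop-out bias.* It is protected when loss depends on baseline drinking, which it conditions on. If loss depends on the 3-month outcome differently by arm, both models are biased and ANCOVA more so.
- *Biased drop-out is to be expected here.* Nothing in the plan documents either mechanism, and the 3-month telephone procedures are the same in both arms.
- *The completer comparison is idle.* The baseline comparison and logistic analyses inform the GEE weights; they just do not trigger the switch.
- *The GEE recovers those lost.* Both branches use completers' 3-month outcomes only, so they differ in model and weighting.

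The effect size is also open. The sample-size text speaks of a large effect in one paragraph and a medium one in the next. At d = 0.8, arm-by-time power is at least 0.96 even at r = 0.3 and 30% loss, so the power contrast matters for a medium effect. Skewed outcomes, which the plan anticipates, would alter the figures.

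**Conclusion.** The point holds. The inference from non-significant drop-out differences to representative completers is invalid, and the drop-out rule is not reconciled with the ANCOVA named as primary and principal.

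The case for naming ANCOVA rests on precedence in the plan's own text and on power, not on general freedom from bias. For a medium effect, the claim of more than 80% power with loss approaching 30% holds for arm-by-time only if r is about 0.5 or higher. Under ANCOVA it holds at nearly any r. Where the groups lose equal proportions, the drop-out test says nothing useful about either bias mechanism. The sizes depend on the assumed d, r, drop-out slopes, normality and two-sided testing. The faulty inference and the missing precedence do not. This should be settled before analysis; it does not affect the planned 180.

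**What to change.** - Delete the drop-out-rate rule and the statement that completers are then representative. Keep the drop-out and completer/non-completer comparisons as description.
- State that, for each primary outcome, the one governing analysis is the 3-month ANCOVA with arm, baseline value of the outcome and MINI randomisation stratum, fitted to participants with a 3-month value.
- The plan also adds covariates found to differ at baseline. Move models with such covariates to sensitivity analyses, so that the primary terms are fixed in advance.
- Label the three-way mixed AN(CO)VA secondary.
- Run the weighted GEE as a sensitivity analysis whatever the drop-out tests show, with weight 1/(1 − estimated drop-out probability) and an arm-by-baseline-drinking term in the drop-out model. State that weighting on baseline variables does not remove bias from loss that depends on the unobserved 3-month outcome.

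The cost is SAP wording and minor programming. Baseline drinking and the MINI stratum are already collected in both arms, so no new data are needed and the sample size is unchanged.

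### The GEE fallback is said to remove any bias from drop-out that is not completely at random, which holds only under missing at random with a correct drop-out model; the completer weight is also misdescribed

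*Combined protocol and SAP*

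**What the plan says.** All of this is in the Statistical Analysis section of the combined protocol and SAP.

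- **Trigger.** Drop-out is compared across the four arm-by-severity groups. If no differential drop-out by severity, arm or their interaction is significant, the loss is treated as random and a mixed-design AN(CO)VA is used. If drop-out differs so that data are judged not missing completely at random, "then we will utilize a generalized estimation equation (GEE) approach, which should provide an unbiased estimate of the intervention effect".
- **Scope claimed.** "GEE utilizes inverse probabilities to correct for any bias associated with NMCAR".
- **Weight.** The same sentence continues: "participants who are Completers weighted with the drop-out probabilities of participants" who are alike at baseline.
- **Source of the weights.** "These weighting values will be estimated from the logistic analyses described above". Those analyses, under Checks for non-Response Bias, use baseline data: "these groups will be compared on Baseline values to determine which, if any, are significant systematic" predictors of completion.
- **Non-completers.** They "will be considered to have missing data for that assessment and will not be included in the analysis of intervention effectiveness".

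The section does not name missing at random, require the drop-out model to be correct, write the weight as one over the probability of completion, or plan an analysis under not-at-random drop-out.

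**The concern.** There are two separate problems.

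**The property claimed.** Data that are not missing completely at random may be missing at random (drop-out explained by recorded variables) or missing not at random (drop-out still related to the unseen outcome). Inverse-probability weighting is consistent only in the first case, and only if the drop-out model is right. Here that model contains baseline variables only. A veteran who stops answering because drinking has worsened since baseline gets no correction from it. The plan itself makes such loss plausible: it allows for 20% to 30% loss to follow-up and, under Screening Interview, describes this population as hard to keep in contact with.

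**The weight.** If p is the probability of dropping out, a completer should carry 1/(1−p). Taken literally, the sentence gives p. Combined with its mention of inverse probabilities, it could be read as 1/p, which down-weights exactly those completers who resemble the drop-outs. Neither is the correct weight.

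At stake is the estimate for both primary outcomes in the situation where missing data threaten it most.

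**Working it through.** **Figures in the plan.** The only stated figures tied to drop-out are in the power table: 0.84, 0.82 and 0.78 with 72, 68 and 63 completers per arm. With d = 0.5 (assumed, since the plan says only medium) and a two-sided 5% level (sidedness is not stated), the noncentral t gives 0.846, 0.825 and 0.795, all within 2 points. The table is not in dispute. It supplies the loss rates and the 68 per arm used below.

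**Step 1: what correct weights leave behind.** Suppose non-completers in one arm drink D more per drinking day than completers alike on every modelled baseline variable. The weighted mean for that arm is then too low by loss × D. D is not in the documents, so it is an assumption:

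| Loss | D = 1 drink | D = 2 drinks |
|---|---|---|
| 20% | 0.20 | 0.40 |
| 25% | 0.25 | 0.50 |
| 30% | 0.30 | 0.60 |

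These values bias the arm difference in full if D applies in one arm only. They cancel if loss and D are equal in both arms.

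**Step 2: simulation.** 400,000 participants, no treatment effect, two thirds with alcohol use disorder (AUD; the plan's 2:1 mix). Assumed: baseline b = N(0,1) + 0.5 × AUD; outcome y = 0.6b + N(0, SD 0.8); logit of drop-out −1.2 in TAU, and −1.3 + b (at random) or −1.3 + y (not at random) in TAU+RA. Drop-out was 23% against 31%, and 23% against 29%. The drop-out model used arm, b, their interaction and severity. Spurious arm difference in SD units:

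| Weight | At random, weighted means | At random, ANCOVA | Not at random, weighted means | Not at random, ANCOVA |
|---|---|---|---|---|
| none | −0.17 | 0.00 | −0.24 | −0.16 |
| 1/(1−p) | 0.00 | 0.00 | −0.16 | −0.16 |
| p | +0.17 | 0.00 | −0.05 | −0.17 |
| 1/p | −0.63 | 0.00 | −0.46 | −0.15 |

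The ANCOVA contained b and severity. Not at random, it stays biased under every weight. The −0.05 for p is two errors partly offsetting, not a correction.

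**Step 3: effect on the error rate.** For a spurious 0.15 SD with 68 per arm, the shift is 0.15 × √(68/2) = 0.875. Two-sided rejection is Φ(−1.96 + 0.875) + Φ(−1.96 − 0.875) = 0.139 + 0.002 ≈ 14%.

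**Step 4: the weight, in a two-stratum example.** Assumed: means of 6 (AUD) and 4 (risky) drinks in both arms, so no true effect; drop-out 25%/25% in TAU and 40%/10% in TAU+RA. The true mean, and the TAU mean under any of these weights, is (2/3)(6) + (1/3)(4) = 5.33. TAU+RA completers form shares (2/3)(0.6) = 0.4 and (1/3)(0.9) = 0.3.

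| Weight | TAU+RA mean | Arm difference |
|---|---|---|
| none | (0.4×6 + 0.3×4)/0.7 = 5.14 | −0.19 |
| p | (0.16×6 + 0.03×4)/0.19 = 5.68 | +0.35 |
| 1/p | (1×6 + 3×4)/4 = 4.50 | −0.83 |
| 1/(1−p) | (0.667×6 + 0.333×4)/1 = 5.33 | 0.00 |

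With milder drop-out (20%/20% against 35%/20%) the differences are −0.10, +0.15, −0.37 and 0.00.

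These figures compare arms without severity. With severity in the model, the comparison is 6 − 6 and 4 − 4 within strata, so the difference is 0.00 under every weight.

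**The case against.** The strongest defence has three parts.

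1. **The weight sentence is loose prose.** It opens with inverse probabilities, and the logistic models it draws on yield the probability of completion as readily as that of drop-out. This stands: a wording slip is the likelier explanation. The text should still be corrected, because no literal reading of it gives 1/(1−p).

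2. **The plan's own model absorbs most of the weight error.** Severity is a design factor and the baseline outcome is a covariate. A reader might infer from the −0.19, +0.35 and −0.83 drinks that the weights as written would leave the trial worse off than no weights. The documents do not support that: in the example the biases vanish once severity is in the model, and in the at-random simulation ANCOVA with every drop-out predictor was unbiased under all four weights. The protection is incomplete, however. Beyond severity and baseline drinking, covariates enter because they differ between groups, not because they predict drop-out, and the covariates of the GEE model are not listed.

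3. **The claim is hedged and the trigger is observed.** The plan says that the method should be unbiased, and the switch follows drop-out differences by arm and severity, which are recorded. This softens the first statement but not the second, which covers any bias. A difference seen across recorded groups also does not show that those groups explain all of the drop-out.

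**Conclusion.** Wrong as written, on both counts, but with unequal weight.

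The substantive fault is the unconditional statement about bias. It holds only if drop-out is missing at random given the modelled baseline variables and the drop-out model is correct. Under the assumed not-at-random mechanism about 0.15 to 0.17 SD of spurious effect survives both baseline adjustment and correct weighting, and 0.15 SD takes a 5% test to about 14%. These sizes rest on assumed mechanisms; the documents give only the loss rates, sample sizes and severity mix.

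The weight is a lesser fault, probably of wording. It biases the arm difference mainly when a predictor of drop-out is left out of the outcome model or that model is wrong.

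A reader might also infer that the fallback is biased whenever it is used. That is not shown: with correct weights, a correct drop-out model and data missing at random, it is consistent. The power table is unaffected.

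**What to change.** 1. Define the completer weight as 1 / Pr(completion | arm, severity, baseline QDS values, other baseline predictors of completion). The planned logistic models already supply this probability.
2. Replace the statement about bias with one limited to data missing at random given those variables, with a correctly specified drop-out model.
3. Add a not-at-random sensitivity analysis for both primary outcomes. One option is a delta-shift (tipping-point) analysis: shift non-completers' outcomes in steps, separately by arm, until the conclusion changes. Use multiple imputation or another method that carries the imputation uncertainty. Filling in baseline drinking as a single value would understate that uncertainty.

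The cost is a few sentences in the SAP, a little extra analysis, and a less favourable statement about bias. No new data are needed.
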